12.3. Statistical Analysis of Safety Outcomes

Adverse event rates will be modeled using Poisson regression with a natural logarithm link function. If over dispersion is identified, a negative binomial model will be used instead. Incidence rate ratios and 95% confidence intervals will be reported. Differences in baseline to 3-month and 6-month change in vital signs and 12-lead ECG will be assessed using Student’s two-sample t-test.

12.4. Study Power

A total of n=90 subjects will be randomized to receiving either IN glulisine (n=45) or placebo (n=45) two times daily. The study is powered on the three primary outcomes, ADAS-Cog 13, CDR-SOB, and FAQ.

	Control Group Mean	Standard Deviation	Minimum Detectable Difference	Power
ADAS-Cog 13	19.2	4.6	3	88.426
CDR-SOB	7.9	1.3	1.5	99.972
FAQ	11.56	3.6	2	74.100

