Primary Objective: To measure the chronic effects of IN insulin glulisine on cognition and function in subjects with aMCI and probable mild AD over a 6 month period.		
Secondary Objectives:		

 To measure the effect of IN insulin glulisine on mood in subjects with aMCI and mild AD over a 6 month period. To measure the safety and efficacy of IN glulisine in aMCI and mild AD subjects with non-insulin dependent diabetes over a 6 month period. 		
Exploratory Objectives:		

 To measure the effect of IN delivery of insulin glulisine on parieto-temporal and posterior cingulate/precuneus glucose metabolism in subjects with aMCI and mild AD over a 6 month period. To measure the chronic effect of IN delivery of insulin glulisine on AD-specific cerebrospinal (CSF) biomarkers (Abeta42, tau, and phosphotau) in subjects with aMCI and mild AD over a 6 month period. To measure the chronic effect of IN delivery of insulin glulisine on sleep in subjects with aMCI and mild AD over a 6 month period. To measure the chronic effect of IN delivery of insulin glulisine on olfaction in subjects with aMCI and mild AD over a 6 month period. 		
STUDY DESIGN		
Study Type	Safety	
Control Type	Placebo	
Study Indication Type	Treatment	
Blinding Schema	Double-Blind	
Device	Pressurized Olfactory Delivery (POD) device	
Study Design	Randomized, double-blinded control	
Planned Duration of Subject Participation	8 months	
ENDPOINTS	Primary	
 ADAS-Cog 13 CDR-SOB FAQ
	Secondary	
 Digit Span Forward

		
 • Trailmaking Test Parts A&B • Controlled Oral Word Association Test (COWAT) • Animal Naming • Weschler Memory Scale (WMS) • Geriatric Depression Scale (GDS)
	Exploratory	
 • CSF Abeta, tau, phosphotau • FDG-PET metabolism posterior parietotemporal, posterior cingulate, and precuneus regions • Sleep questionnaire/Epworth Sleepiness Scale (ESS) • Alberta Smell Test
INVESTIGATIONAL PRODUCTS, DOSE AND MODE OF ADMINISTRATION		
Investigational Product	Glulisine 20 IU/IN (.1ml/10 units IN in each nostril) BID	
Placebo	Sterile Normal Saline 20 IU/IN placebo (.1ml IN in each nostril) BID	
SUBJECT SELECTION		
Targeted Accrual	Approximately 90 randomized subjects. We estimate will need to consent 130 participants in order to reach this goal.	

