7.2. Early Withdrawal

If subject withdraws from the study after the screening visit, but before visit 3, no further evaluations are necessary. If subject withdraws from the study after visit 3, all safety assessments will be performed (see section 7.3).

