9.2. Prohibited Medications

Subjects taking prohibited medications at time of screening will not be allowed to participate in study, unless such treatment is discontinued within 30 days. These medications include anticholinergics, and centrally acting antihistamines (e.g. Benadryl), opiates, benzodiazepines, barbiturates, neuroleptics, muscle relaxants, and insulin. For randomized subjects who take a prohibited med (episodic or PRN) will be considered for study continuation on an individual basis. Randomized subjects who take a prohibited med (long-term or for >7 days per concomitant illness/episode) will be withdrawn from study. Randomized subjects needing to initiate a conditional medication or alter dose of conditional medication during study will be considered on an individual basis.

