12. DATA ANALYSIS AND STATISTICAL CONSIDERATIONS

12.1. Analysis Overview

Measures of central tendency and spread will be computed for the study population and by treatment group for each outcome variable. These summaries will describe patient characteristics, confirm that randomization produced a balanced design, and confirm that the planned analyses are appropriate for the distribution of the outcome variables.

Missing data are expected to be minimal. Therefore, the primary analyses will follow an intent-to-treat principal and include all randomized subjects regardless of intervention compliance and missing data. We will use linear mixed models, an analytic approach that can accommodate unbalanced data and use all available observations in the analysis by assuming data are missing at random. Sensitivity analyses will include evaluation of missing assumptions using pattern mixture models and multiple imputation and a per-protocol approach to accommodate subjects who do not adhere to the intervention protocol.

All statistical tests will be conducted in SAS Version 9.4 and will be evaluated using a two-sided 0.05 level of significance.

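### The power table counts all 45 subjects per arm as evaluable and makes no allowance for loss after randomisation, so its t-test powers hold only with complete data

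*Combined protocol and SAP*

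**What the plan says.** **Sample size and power.** Section 12.4 opens with "A total of n=90 subjects will be randomized to receiving either IN glulisine (n=45) or placebo (n=45) two times daily" and says the study is powered on three primary outcomes. Its rows give control mean, SD, detectable difference and power: "ADAS-Cog 13 19.2 4.6 3 88.426", "CDR-SOB 7.9 1.3 1.5 99.972" and "FAQ 11.56 3.6 2 74.100". It names neither the test nor the time point, and gives no attrition figure. Section 12.1 says that tests "will be evaluated using a two-sided 0.05 level of significance".

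**Allowance for loss.** The only allowance is under Targeted Accrual in the Protocol Summary, where the goal is about 90 randomised: "We estimate will need to consent 130 participants in order to reach this goal".

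**Leaving the study.** Section 9.2: "Randomized subjects who take a prohibited med (long-term or for >7 days per concomitant illness/episode) will be withdrawn from study". Section 10.2 also lets the investigator end participation for adverse events, intolerance, protocol violations or other reasons. Section 7.2: "If subject withdraws from the study after visit 3, all safety assessments will be performed". In the neuropsychological assessment table of Section 7.4, the Early Withdrawal column is marked for GDS and C-SSRS only. ADAS-Cog 13, CDR and FAQ are marked at Visits 2, 7 and 10.

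**On the other side.** Section 5.2 keeps measuring patients who stop treatment where feasible and analyses them as randomised. Section 12.1 anticipates little missing data, without a number. It plans a linear mixed model on all available observations under missing at random, with pattern-mixture and multiple-imputation sensitivity analyses.

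**The concern.** A power figure computed at the number randomised is the power of the trial only if every randomised subject supplies the outcome. The move from 130 consented to 90 randomised happens before randomisation and gives no protection afterwards. The protocol provides for withdrawal from the study, and its withdrawal schedule omits all three primary outcomes. A subject who leaves between weeks 12 and 24 then has no scheduled week-24 value. One who leaves before week 12 has no post-baseline value at all.

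At stake is how far the stated powers can be relied on. FAQ has little to spare, and ADAS-Cog 13 has a modest margin over 80% that a moderate loss would use up.

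**Working it through.** **Inputs.** Two-sided alpha 0.05 (Section 12.1). From Section 12.4: 45 per arm, and SD and difference of 4.6 and 3 (ADAS-Cog 13), 1.3 and 1.5 (CDR-SOB), 3.6 and 2 (FAQ). The documents give no loss rate, so 10%, 15% and 20% are assumptions, taken as equal in both arms.

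**Formula.** Two-sample t-test with n evaluable per arm: noncentrality λ = difference / (SD × √(2/n)), degrees of freedom 2n − 2. Power is the probability that a noncentral t with parameter λ exceeds the two-sided critical value in absolute size.

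**Step 1: reproduce the table at n = 45.** √(2/45) = 0.2108; 88 degrees of freedom; critical value 1.987.

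| Outcome | λ | Computed power | Printed |
|---|---|---|---|
| ADAS-Cog 13 | 3 / (4.6 × 0.2108) = 3.09 | 86.426% | 88.426 |
| CDR-SOB | 1.5 / (1.3 × 0.2108) = 5.47 | 99.972% | 99.972 |
| FAQ | 2 / (3.6 × 0.2108) = 2.64 | 74.100% | 74.100 |

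Two rows match to every printed digit. ADAS-Cog 13 differs by exactly 2.000 points with the other digits the same, which looks like a one-digit slip. That is a separate matter. A one-sided test does not fit (92.3% for ADAS-Cog 13, 83.4% for FAQ). The table is therefore a two-sided t-test with 45 evaluable per arm and no loss.

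**Step 2: put in an assumed loss d, with n = 45 × (1 − d).**

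| Assumed loss | n per arm | ADAS-Cog 13 | CDR-SOB | FAQ |
|---|---|---|---|---|
| 0% | 45 | 86.4% | 99.97% | 74.1% |
| 10% | 40.5 | 82.6% | 99.9% | 69.5% |
| 15% | 38.25 | 80.4% | 99.9% | 66.9% |
| 20% | 36 | 77.9% | 99.8% | 64.2% |

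Measured from the computed zero-loss values, the cost to ADAS-Cog 13 is 3.8 / 6.0 / 8.5 points and to FAQ 4.6 / 7.2 / 9.9 points. Measuring ADAS-Cog 13 from the printed 88.426 would wrongly charge 2 further points to attrition.

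**Step 3: where ADAS-Cog 13 crosses 80%.** At 38 per arm the power is 80.1%; at 37 it is 79.0%. The crossing is at 1 − 37/45 = 17.8%, about 18% loss.

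**The case against.** The strongest reply has four parts.

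- **Missing data are addressed.** Section 12.1 anticipates little missing data and plans sensitivity analyses. This stands as a disclosed assumption, but it has no number or stated basis, and the power section does not carry it through.
- **Stopping treatment need not lose the outcome.** Section 5.2 continues follow-up where feasible. This stands for patients who only stop treatment. It does not settle the position of those whom Section 9.2 or 10.2 removes from the study, for whom Sections 7.2 and 7.4 schedule no primary outcome.
- **The planned analysis is not this t-test.** The Section 12.2 model adjusts for age and baseline score, uses weeks 12 and 24, and analyses three outcomes jointly. If the table's SDs describe raw scores (not stated), multiplying them by √(1 − r²) for an assumed baseline correlation r gives, at 36 per arm, ADAS-Cog 13 81.6% and FAQ 68.3% for r = 0.3, and 88.3% and 76.6% for r = 0.5. Conversely, testing only the arm-by-week interaction could lower power. This part stands: the percentages above belong to the table's calculation.
- **CDR-SOB is practically unaffected.** This stands.

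A reader might infer that the trial will miss its stated power, that those powers are an upper limit for the planned analysis, or that usual attrition takes ADAS-Cog 13 below 80%. The documents support none of these. They give no loss rate, the planned model's power is not computed and could lie on either side, and ADAS-Cog 13 remains above 80% at 15% loss. Nor is attrition the cause of the low FAQ figure.

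**Conclusion.** The point holds in a limited form. The Section 12.4 powers require complete data on all 90 subjects. The protocol gives no expected loss rate, although it provides for withdrawals at which the primary outcomes are not scheduled. Within an assumed 10 to 20% loss, the effect on the table's own test is about 4 to 9 points for ADAS-Cog 13, 5 to 10 points for FAQ, and negligible for CDR-SOB. This rests on the table's SDs and differences, on equal loss in both arms, and on counting only subjects who have the outcome. Week 24 as the relevant time point is inferred from Sections 4.1 and 12.2; the finding of no allowance does not depend on it. Week-12 data and covariate adjustment in the mixed model may offset part of the loss. The matter is worth correcting because the stated powers are figures that readers will rely on; it does not show that the trial is too small.

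**What to change.** 1. Keep n = 90. State an expected missing rate for the primary outcomes, with its basis, and name the test and time point of the power table.
2. Restate the powers at the evaluable number beside the zero-loss figures. In the order ADAS-Cog 13 / CDR-SOB / FAQ, 40 per arm gives 82.1 / 99.9 / 68.9% and 36 per arm gives 77.9 / 99.8 / 64.2%. Use 86.4%, not 88.426%, as the zero-loss value for ADAS-Cog 13.
3. Say that these are t-test figures and that the planned mixed model may recover part of the loss.
4. Reconcile Section 5.2 with Sections 7.2, 7.4 (assessment table), 9.2 and 10.2, so that it is clear whether ADAS-Cog 13, CDR and FAQ are still collected after withdrawal.

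Cost: slightly less favourable stated figures and a short protocol clarification. No extra patients are needed.

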12.2. Statistical Analysis of Efficacy Outcomes

Previous research has shown that the primary outcomes (ADAS-Cog 13, CDR-SOB, and FAQ) to be highly correlated. Therefore, to increase power and account for this correlation, the primary analysis will be a multivariate, linear mixed-effects regression. Specifically, the change in cognition and function measures between baseline and week 12 and between baseline and week 24 will serve as the primary outcome variables. We will include intervention arm, intervention week, intervention arm*week, age, and baseline test scores as fixed effects. The efficacy of intranasal (IN) insulin on cognition and function will be tested on the intervention arm*week interaction. Age and baseline test scores are included because of the possibility of unequal baseline values. Random intercept effects will be included to account for the nested structure of the data, multiple outcomes and observation points.

First, the assumptions of such a model will be verified. That is, the dependent variables will be tested for: (1) multivariate normality, (2) homoscedasticity, (3) equality of covariance matrices, and (4) independent observations. These outcome variables have been analyzed after log-transformation in previous studies because they have a distribution skewed to the right. We will confirm that this transformation is suitable for our study. If outcome variables are log-transformed, efficacy measures will correspond to percent change of cognitive outcomes.

To protect against type I error, efficacy of IN insulin will be considered if an overall cognitive decline is observed relative to placebo. Efficacy measures for composite cognitive and functional decline with corresponding 95% confidence intervals and p-values will be reported.

For the analysis of secondary cognition and function measures (Digit Span, Trailmaking, COWAT, Animal Naming, and WMS), secondary mood measure (GDS), and exploratory smell measure (AST) we will follow the same approach as for the primary outcomes. We have not included these tests as primary endpoints because they measure more specific effects of AD language, memory, mood, or olfaction impairment and, therefore, may be less sensitive to overall cognitive change in MCI/AD patients. Each outcome measure will be tested in its own linear mixed-effects regression model with measures from baseline to week 12 and baseline to week 24 as the outcome variables. The efficacy of IN

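### The power table in section 12.4 is not the power of the arm-by-week test that section 12.2 makes primary, and its ADAS-Cog 13 entry (88.426) recomputes to 86.426

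*Combined protocol and SAP*

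**What the plan says.** Section 12.4 states that "A total of n=90 subjects will be randomized to receiving either IN glulisine (n=45) or placebo (n=45) two times daily" and that "The study is powered on the three primary outcomes, ADAS-Cog 13, CDR-SOB, and FAQ". Its table has one row per outcome:

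| Outcome | Control mean | SD | Difference | Power (%) |
|---|---|---|---|---|
| ADAS-Cog 13 | 19.2 | 4.6 | 3 | 88.426 |
| CDR-SOB | 7.9 | 1.3 | 1.5 | 99.972 |
| FAQ | 11.56 | 3.6 | 2 | 74.100 |

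The section names no test, time point, correlation or allowance for loss. Section 12.1 sets the error rate: all tests "will be evaluated using a two-sided 0.05 level of significance".

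Section 12.2 says that "the primary analysis will be a multivariate, linear mixed-effects regression". The outcome variables are the "change in cognition and function measures between baseline and week 12 and between baseline and week 24", and arm, week and their interaction are all in the model. The test is stated plainly: "The efficacy of intranasal (IN) insulin on cognition and function will be tested on the intervention arm*week interaction". Later the same section adds that "efficacy of IN insulin will be considered if an overall cognitive decline is observed relative to placebo".

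**The concern.** There are two separate points. First, one of the three printed powers does not follow from its own row, although the other two do. Second, the rows behave like separate comparisons of two group means, while the planned test concerns whether the arm difference changes between week 12 and week 24. These are different contrasts with different power.

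Section 12.4 is the only support the plan gives for n=90, and it is where a reader will turn to interpret a null result. Someone who takes 74 to 99.97% as the power of the primary test could read a non-significant interaction as evidence against the drug, when that test may have had little chance of detecting a benefit that appeared early and persisted.

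**Working it through.** **Inputs.** 45 per arm, the SDs and the differences come from section 12.4. Two-sided alpha of 0.05 comes from section 12.1.

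**Step 1: reproduce the table.** The two-sample t-test has df = 45 + 45 − 2 = 88, critical value 1.987 and noncentrality difference / (SD × √(2/45)). Power comes from the noncentral t distribution.

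| Outcome | Noncentrality | Recomputed (%) | Printed (%) |
|---|---|---|---|
| ADAS-Cog 13 | 3 / (4.6 × 0.2108) = 3.094 | 86.426 | 88.426 |
| CDR-SOB | 1.5 / (1.3 × 0.2108) = 5.473 | 99.972 | 99.972 |
| FAQ | 2 / (3.6 × 0.2108) = 2.635 | 74.100 | 74.100 |

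Two rows agree to all three decimals, which identifies the method. The third differs in one digit.

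**Step 2: look for another explanation of 88.426.**

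- Rounded inputs: it would need an SD of 4.459 or a difference of 3.095, both outside rounding of 4.6 and 3. The most favourable pair (difference 3.0499, SD 4.55) gives 88.193.
- Normal approximation: 87.151, 99.978 and 75.025 for the three rows.
- One-sided t-test: 92.289, 99.992 and 83.398.
- Sample size: 47 per arm gives 87.868 and 48 gives 88.536 for ADAS-Cog 13, while FAQ moves to 75.959 and 76.846. No n from 36 to 51 per arm fits all three rows.

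**Step 3: what the planned test measures.** The outcomes are already changes from baseline and there are only two follow-up weeks. With arm as a separate term, the arm-by-week interaction is the week 24 arm effect minus the week 12 arm effect. Let d be the table difference at week 24, f the share of it already present at week 12, and r the correlation between the two change scores. For one outcome, with the table SD at each week:

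- contrast = d × (1 − f)
- SD of the contrast = SD × √(2 × (1 − r))

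The documents give neither f nor r. Both are assumptions here. For example, ADAS-Cog 13 with f = 0.5 and r = 0.5 has contrast 1.5 and SD 4.6, which gives 33.4%. Power (%) with 45 per arm, for r = 0.5 to r = 0.8:

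| Share at week 12 | ADAS-Cog 13 | CDR-SOB | FAQ |
|---|---|---|---|
| None | 86.4 to 99.8 | above 99.9 | 74.1 to 98.5 |
| Half | 33.4 to 67.7 | 77.2 to 99.0 | 25.6 to 54.0 |
| Three quarters | 11.9 to 22.7 | 27.3 to 57.1 | 10.0 to 17.8 |
| All, and held | 5.0 | 5.0 | 5.0 |

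The last row needs no value for r, because the contrast is zero.

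**Step 4: joint modelling.** The three outcomes were standardised by the table SDs, with an assumed between-outcome correlation of 0.5 to 0.8 and r again 0.5 to 0.8. With half the effect at week 12, power is 51 to 95% for a composite (mean) contrast and 60 to 99% for a three-degree-of-freedom Hotelling test. With none at week 12, both are 97.8% or more. With all of it present and held, both are 5%. These are two simple readings of the multivariate model, not a fit of the full model.

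**The case against.** **The digit may not be in the protocol at all.** The table was read from a PDF, and 88.426 and 86.426 differ by one character. This stands: the entry must be checked against the source document, and it is inconsequential either way.

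**The table can coincide with the planned test.** With no effect at week 12 and a correlation of 0.5, the interaction gives exactly the t-test values (86.4 and 74.1). That is true, but it is a special case that section 12.4 does not assume.

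**The primary contrast is not settled.** Section 12.2 also refers to an overall decline relative to placebo and to composite measures. If the contrast were the mean of the two weeks, an effect fully present at week 12 and held would give 89.7 to 94.2% for ADAS-Cog 13 and 78.4 to 85.3% for FAQ, on the same assumptions, instead of 5%. This is the strongest point. It does not rescue section 12.4, which says nothing about which contrast it serves; it shows why the contrast must be named.

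**The illustrations rest on assumptions.** This also stands. The control means look like score levels, so the table SDs may not be SDs of change. Adjustment for age and baseline score, and the possible log transformation, are left out. The percentages show how far power can move and are not estimates for this trial.

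**Conclusion.** Both parts hold. The ADAS-Cog 13 entry should be 86.426 on the method that reproduces the other two rows, 2.0 points below the printed value; power stays above 80% and n is unaffected. This part uses only the plan's own inputs.

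The table does not give the power of the arm-by-week test. That conclusion follows from sections 12.2 and 12.4 alone. Its size depends on assumed values for the week 12 share and the correlations: the table may be too low if the effect comes late, or far too high if much of it is present by week 12. Joint modelling does not remove that dependence. The documents do not show that the trial is underpowered, and that is not claimed here.

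**What to change.** In section 12.4:

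1. Check 88.426 against the source document and, if it is printed so, correct it to 86.426.
2. State that the table is for a two-sample t-test at two-sided 0.05 with 45 evaluable per arm, and that it is not the power of the arm-by-week test.
3. Name the contrast that will decide efficacy, consistent with section 12.2. Give its power with the assumed share of the effect at week 12 and the between-week correlation declared, and the between-outcome correlation if the test is joint.
4. Optionally, add rows for an assumed loss. For example, 40 or 36 per arm gives 82.1% or 77.9% for ADAS-Cog 13 and 68.9% or 64.2% for FAQ. These sample sizes are illustrations, since the plan states no dropout rate.

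The cost is some rewording and one short calculation. Sample size, visits and data collection do not change.

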13. STUDY CONDUCT CONSIDERATIONS

13.1. Regulatory and Ethical Considerations, Including the Informed Consent Process

The study will be conducted in accordance with GCP. Subject privacy requirements will also be observed as well as the fundamental concepts of the Declaration of Helsinki (e.g. IRB approval of the study, obtaining informed consent from all subjects, and meeting reporting requirements).

